APPENDIX 4 RESPONSE EVALUATION IN PTL

Subjects with PTL will be evaluated for response using a 2 compartment model, where the 2014 Lugano Classification will be used for systemic lesions and the IPCG criteria will be used for CNS lesions.

Table 1: **Revised Criteria for Response Assessment: 2014 Lugano Classification**

Response and Site	PET-CT-Based Response	CT-Based Response
Complete		
Lymph nodes and extralymphatic sites	Complete metabolic response Score 1, 2, or 3* with or without a residual mass on 5PST It is recognized that in Waldeyer's ring or extranodal sites with high physiologic uptake or with activation within spleen or marrow (eg, with chemotherapy or myeloid colony-stimulating factors), uptake may be greater than normal mediastinum and/or liver. In this circumstance, complete metabolic response may be inferred if uptake at sites of initial involvement is no greater than surrounding normal tissue even if the tissue has high physiologic uptake	Complete radiologic response (all of the following) Target nodes/nodal masses must regress to ≤ 1.5 cm in LDi No extralymphatic sites of disease
Nonmeasured lesion	Not applicable	Absent
Organ enlargement	Not applicable	Regress to normal
New lesions	None	None
Bone marrow	No evidence of FDG-avid disease in marrow	Normal by morphology; if indeterminate, IHC negative
Partial		
Lymph nodes and extralymphatic sites	Partial metabolic response Score 4 or 5† with reduced uptake compared with baseline and residual mass(es) of any size At interim, these findings suggest responding disease At end of treatment, these findings indicate residual disease	Partial remission (all of the following) $\geq 50\%$ decrease in SPD of up to 6 target measurable nodes and extranodal sites When a lesion is too small to measure on CT, assign 5 mm \times 5 mm as the default value When no longer visible, 0 \times 0 mm For a node > 5 mm \times 5 mm, but smaller than normal, use actual measurement for calculation Absent/normal, regressed, but no increase Spleen must have regressed by $> 50\%$ in length beyond normal
Nonmeasured lesions	Not applicable	None
Organ enlargement	Not applicable	Not applicable
New lesions	None	None
Bone marrow	Residual uptake higher than uptake in normal marrow but reduced compared with baseline (diffuse uptake compatible with reactive changes from chemotherapy allowed). If there are persistent focal changes in the marrow in the context of a nodal response, consideration should be given to further evaluation with MRI or biopsy or an interval scan	Not applicable
No response or stable disease		
Target nodes/nodal masses, extranodal lesions	No metabolic response Score 4 or 5 with no significant change in FDG uptake from baseline at interim or end of treatment	Stable disease $< 50\%$ decrease from baseline in SPD of up to 6 dominant, measurable nodes and extranodal sites; no criteria for progressive disease are met
Nonmeasured lesions	Not applicable	No increase consistent with progression
Organ enlargement	Not applicable	No increase consistent with progression
New lesions	None	None
Bone marrow	No change from baseline	Not applicable
Progressive disease		
Individual target nodes/nodal masses	Progressive metabolic disease Score 4 or 5 with an increase in intensity of uptake from baseline and/or	Progressive disease requires at least 1 of the following PPD progression:
Extranodal lesions	New FDG-avid foci consistent with lymphoma at interim or end-of-treatment assessment	An individual node/lesion must be abnormal with: LDi > 1.5 cm and Increase by $\geq 50\%$ from PPD nadir and An increase in LDi or SDi from nadir 0.5 cm for lesions ≤ 2 cm 1.0 cm for lesions > 2 cm In the setting of splenomegaly, the splenic length must increase by $> 50\%$ of the extent of its prior increase beyond baseline (eg, a 15-cm spleen must increase to > 16 cm). If no prior splenomegaly, must increase by at least 2 cm from baseline New or recurrent splenomegaly
Nonmeasured lesions	None	New or clear progression of preexisting nonmeasured lesions

(continued on following page)

Response and Site	PET-CT-Based Response	CT-Based Response
New lesions	New FDG-avid foci consistent with lymphoma rather than another etiology (eg, infection, inflammation). If uncertain regarding etiology of new lesions, biopsy or interval scan may be considered	Regrowth of previously resolved lesions A new node > 1.5 cm in any axis A new extranodal site > 1.0 cm in any axis; if < 1.0 cm in any axis, its presence must be unequivocal and must be attributable to lymphoma Assessable disease of any size unequivocally attributable to lymphoma
Bone marrow	New or recurrent FDG-avid foci	New or recurrent involvement

Abbreviations: 5PS, 5-point scale; CT, computed tomography; FDG, fluorodeoxyglucose; IHC, immunohistochemistry; LD_i, longest transverse diameter of a lesion; MRI, magnetic resonance imaging; PET, positron emission tomography; PPD, cross product of the LD_i and perpendicular diameter; SD_i, shortest axis perpendicular to the LD_i; SPD, sum of the product of the perpendicular diameters for multiple lesions.
 *A score of 3 in many patients indicates a good prognosis with standard treatment, especially if at the time of an interim scan. However, in trials involving PET where de-escalation is investigated, it may be preferable to consider a score of 3 as inadequate response (to avoid undertreatment). Measured dominant lesions: Up to six of the largest dominant nodes, nodal masses, and extranodal lesions selected to be clearly measurable in two diameters. Nodes should preferably be from disparate regions of the body and should include, where applicable, mediastinal and retroperitoneal areas. Non-nodal lesions include those in solid organs (eg, liver, spleen, kidneys, lungs), GI involvement, cutaneous lesions, or those noted on palpation. Nonmeasured lesions: Any disease not selected as measured, dominant disease and truly assessable disease should be considered not measured. These sites include any nodes, nodal masses, and extranodal sites not selected as dominant or measurable or that do not meet the requirements for measurability but are still considered abnormal, as well as truly assessable disease, which is any site of suspected disease that would be difficult to follow quantitatively with measurement, including pleural effusions, ascites, bone lesions, leptomeningeal disease, abdominal masses, and other lesions that cannot be confirmed and followed by imaging. In Waldeyer's ring or in extranodal sites (eg, GI tract, liver, bone marrow), FDG uptake may be greater than in the mediastinum with complete metabolic response, but should be no higher than surrounding normal physiologic uptake (eg, with marrow activation as a result of chemotherapy or myeloid growth factors).
 †PET 5PS: 1, no uptake above background; 2, uptake ≤ mediastinum; 3, uptake > mediastinum but ≤ liver; 4, uptake moderately > liver; 5, uptake markedly higher than liver and/or new lesions; X, new areas of uptake unlikely to be related to lymphoma.

*The recommendations from Lugano Classification is to use a 5 point scale to assess the metabolic response in PET-CT based response.

Response Evaluation for systemic lesions in PTL:

CR (Complete Remission)

The designation of CR requires all of the following be met:

- 1) Complete disappearance of all detectable clinical evidence of disease.
 - a) PET-CT-based response: A score of ≤ 3 is considered to represent complete metabolic response.
 - b) CT based response: Target node/nodal masses must regress to ≤ 1.5 cm in LD_i, with no extralymphatic sites of disease
- 2) Organ involvement: Absence of organomegaly
- 3) Bone marrow: No evidence of FDG- avid disease in marrow. If there was evidence of involvement of bone marrow with lymphoma at screening/baseline and a biopsy was performed (PTCL), a bone marrow biopsy will be required to confirm CR.
- 4) The presence of residual symptoms in the absence of detectable disease by imaging does not preclude the designation of CR.

PR (Partial Remission)

The designation of PR requires all of the following:

- 1) PET-CT based response: Score of 4 or 5, provided reduced uptake compared with base line and absence of structural progression development on CT Scan.

- 2) CT based response: $\geq 50\%$ regression in SPD of up to 6 measurable nodal and extranodal lesions
- 3) Splenic and hepatic nodules must regress by $\geq 50\%$ in length beyond normal.
- 4) Bone marrow: reduced uptake compared with baseline. If there is evidence of nodal response but persistent focal changes in the marrow consider further evaluation

SD (Stable Disease)

SD is defined as the following:

- 1) PET-CT based response: no metabolic response, score of 4 or 5 with no significant changes from baseline.
- 2) CT based response: $< 50\%$ decrease from baseline, absence of new lesions
- 3) Bone marrow: no change from baseline.

PD: Relapsed Disease (after CR)/Progressive Disease (after PR, SD)

- 1) PET-CT based response: Score of 4 or 5 with increase in intensity from baseline or interim scan/ or any new FDG avid focus consistent with malignant lymphoma
- 2) CT based response: New node, new or recurrent splenomegaly, progression of existing lesions

Response Evaluation for CNS lesions in PTL:

The IPCG criteria as described in [Appendix 3](#) will be used for PTL patients with CNS lesions.

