 - Nodes should preferably be from disparate regions of the body and should include, where applicable, mediastinal and retroperitoneal areas. A measurable node must have a longest diameter (LDi) > 1.5 cm.
 - Non-nodal lesions include those in solid organs (eg, liver, spleen, kidneys, lungs), GI involvement, cutaneous lesions, or those noted on palpation. A measurable extranodal lesion must have a LDi > 1.0 cm and may be included in the 6 representative, measured lesions (eg, hepatic nodules).
- A sum of the product of the diameters (SPD) will be calculated for all target lesions (CNS and non-CNS) and recorded as the baseline SPD. The baseline SPD will be used as reference to further characterize any objective tumor regression in the measurable dimension of the disease.

CT Measurements

For subjects staged with CT, up to 6 of the largest target nodes, nodal masses, or other lymphomatous lesions that are measurable in 2 diameters (LDi and shortest diameter) should be identified from different body regions representative of the patient's overall disease burden and include mediastinal and retroperitoneal disease, if involved. A measurable node must have a LDi greater than 1.5 cm. Measurable extranodal disease (eg, hepatic nodules) may be included in the 6 representative, measured lesions. For extranodal measurable lesion the LDi must be greater than 1.0 cm. All other lesions (including nodal, extranodal, and assessable disease) should be followed as non-measured disease (eg, cutaneous, GI, bone, spleen, liver, kidneys, pleural or pericardial effusions, ascites).

Non-Measurable Lesions

Besides small lymph nodes (longest diameter < 10 mm), truly non-measurable lesions include: leptomeningeal disease, ascites, pleural or pericardial effusion, inflammatory breast disease, lymphangitic involvement of skin or lung, or abdominal masses/abdominal organomegaly identified by physical exam that are not measurable by reproducible imaging techniques.

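### Appendix 4 defines PR for PTL in two conflicting ways: the narrative applies the spleen-length criterion to splenic and hepatic nodules, so a subject who meets the 50% SPD rule can still fail PR

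*Protocol*

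**What the plan says.** Protocol Appendix 4 gives PR for systemic PTL lesions in Table 1 and again in a narrative list.

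- **Table 1, CT-based column.** There are two separate requirements. For lesions, the rule is at least a 50% "decrease in SPD of up to 6 target measurable nodes and extranodal sites". For the organ, it is "Spleen must have regressed by $> 50\%$ in length beyond normal". Nodules have no length rule.
- **Table 1, PET-CT column.** PR is a score of 4 or 5 with less uptake than at baseline. Residual masses may be of any size, and organ enlargement is marked as not applicable.
- **Narrative.** "The designation of PR requires all of the following". Item 1 is the PET-CT score. Item 2 is at least 50% "regression in SPD of up to 6 measurable nodal and extranodal lesions". Item 3 begins "Splenic and hepatic nodules must regress by" and sets the threshold at 50% or more of length beyond normal. Item 4 concerns marrow.
- **Section 5.4.1, Measurable Lesions.** An extranodal lesion with longest diameter above 1.0 cm "may be included in the 6 representative, measured lesions (eg, hepatic nodules", which is the example given there.

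Neither the protocol nor the SAP says whether the table or the narrative governs.

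**The concern.** Item 3 has the wording of a spleen criterion but a different subject. A length beyond normal makes sense for an organ with a normal size. For a nodule no normal length is given, and the nearest literal reading is that the nodule must halve in length. A hepatic nodule chosen as a target lesion then faces two thresholds in a list where all items must hold: its share of the SPD in item 2 and its own length in item 3. The comparison sign also changes, from more than 50% in the table to at least 50% in the narrative.

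The organ criterion meanwhile drops out. The narrative CR asks for absence of organomegaly and the narrative PD lists new or recurrent splenomegaly, but no narrative PR item mentions spleen size.

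PR feeds the primary endpoint in PTL (BICR-assessed ORR, Protocol 8.3.1 and SAP 4.1), as well as investigator-assessed ORR and both versions of DOR. Two readers who start from different halves of Appendix 4 could classify the same scan differently.

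**Working it through.** **Inputs.** The PR rules are those of Appendix 4. The target-lesion rule is in Section 5.4.1. The PTL cohort size of 20, the 14% reference rate and the exact intervals are in Protocol 8.1 and SAP Section 5. Lesion sizes below are illustrative.

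**1. The plan's own intervals.** The Clopper-Pearson limits are the 2.5% quantile of Beta(x, n - x + 1) and the 97.5% quantile of Beta(x + 1, n - x). With n = 20, x = 6 gives 11.9% to 54.3% and x = 7 gives 15.4% to 59.2%. Both match Table 8.1-1.

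**2. One nodule as the only target lesion.** If both diameters shrink by a factor f, the SPD falls by 1 - f² and the length by 1 - f.

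- A 50% SPD fall needs f = √0.5 = 0.707, a 29.3% fall in diameter.
- A 50% length fall means f = 0.5, a 75% fall in SPD.
- For 30 x 30 mm to 20 x 20 mm, SPD falls by 1 - (20/30)² = 55.6% and length by 1 - 20/30 = 33.3%. Item 2 is met and item 3 is not.
- For 3 x 3 cm to 3 x 1.5 cm, SPD falls by 1 - 4.5/9 = 50% and the longest diameter does not change. Again item 2 is met and item 3 is not.

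If uptake has also fallen, the subject in the third line does not fit narrative SD either, which asks for no metabolic response and less than a 50% decrease. Nothing in the example meets PD. The narrative leaves this subject without a category, although SAP 7.5.1 tabulates BOR by category.

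**3. Several target lesions.** SPD is a sum, so the thresholds in step 2 do not carry over to each nodule. Take a 30 x 30 mm hepatic nodule (900 mm²) and a 40 x 40 mm node (1,600 mm²), total 2,500 mm².

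- The nodule falls to 20 x 20 mm and the node is unchanged: 400 + 1,600 = 2,000, a 20% fall. PR fails on item 2 already.
- The node disappears and the nodule is unchanged: 900, a 64% fall. Item 2 is met and item 3 is not.

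The two rules can conflict at any degree of nodule shrinkage below 50% in length, depending on the other lesions.

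**4. Spleen.** The PD row of Table 1 gives an example in which a 15 cm spleen must exceed 16 cm. From 16 = 15 + 0.5 x (15 - normal), the implied normal length is 13 cm (it is not stated). On the same convention the CT-based PR rule needs a 15 cm spleen to fall below 13 + 0.5 x (15 - 13) = 14 cm. A spleen that stays at 15 cm breaks no narrative PR item but fails the CT-based column.

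**5. Modality.** Section 5.4.1 has PTL response evaluated by FDG-PET/CT or PET/MRI. Under the PET-CT column of Table 1, neither SPD nor spleen length decides PR. If narrative items 1 to 3 are joint, items 2 and 3 both conflict with that column.

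**6. Size per subject.** One subject is 1/20 = 5 percentage points of ORR.

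**The case against.** The strongest reply is that PTL is read by PET. Items 1 and 2 are labelled by modality, so they may be meant as alternatives, with item 3 belonging to the CT-based reading. A reader using the PET-CT column would then never reach item 3. BICR procedure is also left to an imaging charter (Protocol Section 7) that is not among the documents, and central readers may not apply item 3 literally. This stands as a limit on the consequences. It does not remove the contradiction, because the narrative says all items are required, no text says which version governs, and the investigators' criteria are those of Appendix 4.

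A reader might infer three stronger conclusions that the documents do not support.

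- **Every nodule shrinking 29% to 49% in diameter meets PR by SPD and fails item 3.** That band holds only for a sole round nodule or for proportional shrinkage of all targets, as step 3 shows. A nodule that halves in length satisfies both rules.
- **The plan accepts PR with an enlarged spleen that has not shrunk.** That follows from the narrative taken alone. The CT-based column of the same appendix still carries the spleen rule.
- **A countable number of subjects, or the PTL conclusion, would change.** The documents do not say how many PTL subjects have hepatic or splenic lesions. Having such a lesion is not enough in any case: the total SPD must fall by at least 50%, the nodule must shrink by less than half in length, the subject must not be in CR, and the reader must apply item 3 literally. The contrast of 6/20 (lower bound 11.9%) with 7/20 (15.4%) around 14% shows sensitivity to any one subject, not an expected effect.

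**Conclusion.** The contradiction is in the current text and should be corrected. Narrative item 3, followed literally, can deny PR to a subject who meets the SPD rule of Table 1, while the narrative omits the spleen condition that the CT-based column contains. The worked case (SPD down 56%, length down 33%) rests on three assumptions: the nodule is the only target lesion, the narrative items are joint, and item 3 means halving the nodule's length. The number of subjects affected is unknown and could be zero; each one moves the PTL ORR by 5 points. The unsettled choice between PET-CT and CT-based criteria is part of the same problem, since it decides whether item 3 applies at all.

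**What to change.** Reconcile item 3 of the narrative PR list with Table 1:

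- Make the length-beyond-normal criterion refer to the spleen, within the CT-based assessment only, and use one comparison sign in both places.
- State that splenic and hepatic nodules are judged through the SPD when chosen as measured lesions, and are otherwise followed as non-measured lesions. Section 5.4.1 largely says this already.
- State whether the PET-CT or the CT-based criteria govern PR in PTL, and whether narrative items 1 to 3 are joint or alternatives by modality. Without this, moving the spleen rule into a joint list would carry over the conflict with the PET-CT column.
- Align the imaging charter with the corrected text.

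The cost is a short edit to Appendix 4 and a matching check of the charter. No new data are needed. The change should be made before responses are adjudicated.

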APPENDIX 6 TUMOR FLARE

Tumor Flare in CNS tumors:

Tumor flare (TF): Immunomodulatory agents, such as immune checkpoint inhibitors, may be associated with clinical and imaging findings during treatment, suggestive of progressive disease (PD) despite evidence of clinical benefit (tumor flare or pseudo-progression).^{1,2} This phenomenon has been well described with checkpoint blockade therapy in solid tumors, with an incidence of 10% in melanoma and 3% in lung cancer.³ Furthermore, this has also been reported anecdotally in lymphomas.⁴ Pseudoprogression appears as tumor progression or radiographic progression with target lesion size increase. Often it may be associated with mixed responses, which include good response (i.e., shrinkage) but increased tumor size or even new lesion appearance elsewhere. The patient may or may not present with deterioration in clinical symptoms. Considering this finding as PD could lead to patients being prematurely removed from a treatment from which they actually stand to benefit. Therefore it is important to remain cognizant of this effect during treatment.

Few important characteristics observed with TF are outlined below:

- Tumor inflammation is the intended effect of anti-tumor immune therapies, so tumor flare is consistent with eventual benefit. As it is important not to abandon immunotherapy prematurely, these observations have led to development of immune-related response criteria.^{1,4}
- TF may be more clinically evident, i.e. lead to early development of symptoms, in CNS tumors than in tumors of other sites due to their intracranial location.
- TF is indistinguishable from disease progression (thus sometimes called ‘pseudoprogression’), and thus presents a major clinical challenge.

It is ordinarily not possible to determine whether increased neurologic symptoms and/or radiographic findings represent tumor progression or transient TF. Observation, sometimes prolonged, is required to make this determination.

- In some settings, moreover, adverse effects of other concomitant treatment (such as RT) may be equally as likely.
- Less frequently adverse effects of immunotherapy on normal brain tissues may be possible.

In other Central Nervous System trials of nivolumab (alone or with ipilimumab), clinical findings of TF have been highly variable, based on the location of the lesion, including confusion, aphasia, hemiplegia, seizure, etc. Because of this neurologic heterogeneity, we have used the overall diagnostic term “Tumor Flare” in order to capture it systematically in our adverse event database.

Treatment strategies during TF:

- Corticosteroids (e.g. dexamethasone 4-8 mg/day) are generally fairly effective in reversing neurologic dysfunction, perhaps more effective than might be seen with disease progression. They may be tapered as quickly as tolerated (in contrast to systemic IMAEs such as pneumonitis, for which very slow tapering is advised). If acute or severe neurologic deterioration, dexamethasone bolus of 10-20 mg intravenously or corticosteroid equivalent, once, can be considered, followed by a smaller dose for maintenance such as 2-4mg daily, to be rapidly tapered off once neurologic deficits improve.
- If symptoms are moderate to severe, delay of immune treatment is appropriate.
- Generalized effects of increased pressure, including midline shift, hydrocephalus, obliteration of sulci, etc. have also been noted, but are non-specific.
- Imaging changes are sometimes more striking than clinical AEs; if radiographic findings are not associated with clinical deterioration, immune treatment need not be delayed. Cerebral edema on imaging by itself need not be a criteria for drug discontinuation.
- Investigations on potential radiographic features which could assist in discriminating TF from disease progression are in progress.

If surgically accessible, a diagnostic biopsy may be feasible.

- As always, there is concern that a representative sample be obtained.
- A predominance of necrosis, and inflammation is consistent with TF, and very helpful in allaying the concern generated by clinical and imaging changes. Unfortunately, of course, a biopsy may confirm tumor progression.
- In such cases, we would encourage that the immune treatment be resumed.

Every patient is different; consultation with the Medical Monitor and review of the imaging is often useful.

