4.5.6 Nivolumab Treatment Beyond Progression

Evidence indicates a minority of subjects treated with immunotherapy may derive clinical benefit despite initial evidence of PD,⁶¹ eg, due to inflammatory reaction simulating progression (“tumor flare” or pseudoprogression). Pseudoprogression is well described in neuro-oncology, and refers to radiographic enlargement of tumor lesions that would be interpreted as disease progression by conventional response criteria, but upon histologic examination reveals necrosis and/or

inflammation (treatment effect) and not disease progression.⁶¹ A similar phenomenon has been observed in various tumors when treated with immunotherapeutic agents, in which transient enlargement of lesions or appearance of new lesions is attributable to the influx of immune cells. These potential immune treatment effects complicate the evaluation of response and may lead to premature discontinuation of therapy. Furthermore, the time period to pseudoprogression or tumor flare with different immune therapies varies in different malignancies. See [Appendix 6](#) for the management of tumor flare for subjects enrolled in this study.

Subjects treated with nivolumab will be permitted to continue nivolumab treatment beyond initial progressive disease, assessed by the investigator, as long as they meet the following criteria:

- Investigator-assessed clinical benefit
- Tolerance of study drug
- Treatment beyond progression will not delay an imminent intervention to prevent serious complications of disease progression (eg, CNS metastases or from mass effect)
- Subject provides written informed consent prior to receiving additional nivolumab treatment

All other elements of the main consent including description of reasonably foreseeable risks or discomforts, or other alternative treatment options will still apply.

A radiographic assessment/scan should be performed within 8 weeks of initial investigator-assessed progression to determine whether there has been a decrease in the tumor size or continued PD. The assessment of clinical benefit should be balanced by clinical judgment as to whether the subject is clinically deteriorating and unlikely to receive any benefit from continued treatment with nivolumab.

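### Appendix 6, read in order, encourages resuming nivolumab after biopsy-confirmed progression without the conditions of Sections 3.5 and 4.5.6

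*Protocol*

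**What the plan says.** Protocol Section 3.5 lists disease progression among the reasons for which study drug must be stopped, with one exception: the circumstances described in Section 4.5.6.

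Section 4.5.6 explains the exception. Pseudoprogression is enlargement on imaging that, on histology, turns out to be necrosis and/or "inflammation (treatment effect) and not disease progression". Dosing beyond initial investigator-assessed progression is allowed if four conditions are met:

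- the investigator judges that there is clinical benefit;
- the subject tolerates the drug;
- "Treatment beyond progression will not delay an imminent intervention to prevent serious complications of disease progression";
- "Subject provides written informed consent prior to receiving additional nivolumab treatment".

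A follow-up scan is due within 8 weeks. If it shows continued progression, dosing may go on under the same conditions. A second scan is due within 8 weeks of that second progression, and continued progression there means stopping. The section points to Appendix 6 "for the management of tumor flare for subjects enrolled in this study".

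Appendix 6 covers treatment during flare ("If symptoms are moderate to severe, delay of immune treatment is appropriate") and then a possible biopsy of an accessible lesion. One bullet contains two findings in sequence: "A predominance of necrosis, and inflammation is consistent with TF", and then "Unfortunately, of course, a biopsy may confirm tumor progression". The next bullet is "In such cases, we would encourage that the immune treatment be resumed".

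On the minor point, Section 4.5.1 ends 480 mg dosing at progression, unacceptable toxicity, withdrawal of consent or study end. The synopsis, Section 3.1, Table 5.1-2, and SAP Sections 2.1 and 6.2 add a limit of 2 years of treatment.

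**The concern.** The words that open the bullet refer back to something, and the nearest candidate is the sentence about a biopsy that confirms progression. On that reading the appendix encourages re-dosing in exactly the situation where Section 3.5 requires stopping unless the Section 4.5.6 conditions hold. It also does not send the reader back to either section.

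Patient safety is at stake. The bullet speaks of resuming, so it concerns subjects whose dosing has been held, and the appendix advises holding when symptoms are moderate to severe. For a symptomatic subject with a growing intracranial lesion, the imminent-intervention condition is directly relevant; Section 4.5.6 itself gives mass effect as an example. A site that followed the bullet literally would not be prompted to check that condition or to obtain the additional written consent.

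**Working it through.** No arithmetic applies, and the plan gives no figure to reproduce. The check sets the texts side by side.

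1. **What the bullet refers to.** The preceding bullet holds two findings: necrosis and inflammation ("A predominance of necrosis, and inflammation is consistent with TF"), then confirmed progression ("Unfortunately, of course, a biopsy may confirm tumor progression"). The second stands immediately before the resume bullet. By ordinary reading order, the cases meant are those of confirmed progression.

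2. **What was probably meant.** Section 4.5.6 describes pseudoprogression histologically as treatment effect, in contrast to progression. The appendix stresses that immunotherapy should not be abandoned too early because of flare. Resuming fits a biopsy that supports flare. A biopsy that confirms progression falls outside that description, so the necrosis and inflammation sentence is almost certainly the intended reference.

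3. **The literal reading against the governing sections.**

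| Requirement when progression is present | Sections 3.5 and 4.5.6 | Appendix 6 |
|---|---|---|
| Default action | Stop study drug | Resume is encouraged |
| Clinical benefit | Required | Mentioned in the general description of flare; not made a condition of resuming |
| Tolerance | Required | Not stated as a condition of resuming |
| No delay of an imminent intervention | Required | Not stated |
| Written consent before further dosing | Required | Not stated |
| End point for continued dosing | Stop if the second 8-week scan shows continued progression | Not stated |
| Reference back to 3.5 or 4.5.6 | Not applicable | None |

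4. **Whether other text closes the gap.** The scan sequence in Section 4.5.6 does not say what to do with a biopsy result. In the visible text, the Appendix 6 bullet is the only sentence that links a biopsy result to the next nivolumab dose. Because Section 4.5.6 sends sites to this appendix, they can be expected to read it when the question arises.

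5. **Effect on the analysis.** Protocol Section 8.3.1 and SAP Section 4.1 take best overall response only up to the first objectively documented progression or subsequent therapy. Re-dosing after that progression cannot add a responder. The sample size rationale does not depend on it either.

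6. **Minor point.** Section 4.5.1 gives its stopping conditions as a list in which the earliest applies, and the 2-year maximum is not in that list. The limit appears in three other places in the protocol and two in the SAP. The omission is real but easily resolved by the dosing row of Table 5.1-2.

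**The case against.** The strongest reply is that this is a loose pronoun with no practical effect. The passage is about managing flare, the remark about confirmed progression reads as an aside, and the bullet only encourages, whereas Section 3.5 uses mandatory language. The stopping rule in Section 3.5 is not limited to imaging, so it already covers progression shown by biopsy. The four entry conditions in Section 4.5.6 do not depend on a scan. There are further safeguards:

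- The appendix describes flare as occurring despite evidence of clinical benefit.
- It closes by recommending consultation with the Medical Monitor.
- Section 4.5.5 requires that consultation before re-dosing after a delay of more than 6 weeks, and requires stopping when the investigator sees substantial clinical risk.
- Section 3.3.2 points to Sections 3.4.1 and 3.4.2 for steroid use in flare. These are not in the public text, so one cannot say that sites had no other guidance.

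Most of this stands, and it limits the point. A reader might infer that Appendix 6 contradicts or overrides Sections 3.5 and 4.5.6, or that any dosing after progression breaches the protocol. The documents support neither. Section 3.5 carries an explicit exception, Section 4.5.6 permits dosing after progression under conditions, and nothing in Appendix 6 claims precedence.

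The reply does not remove the wording problem. Consultation with the Medical Monitor is described in the appendix only as often useful, and it is mandatory only after the longer delays. Neither that line nor the mention of clinical benefit supplies the intervention and consent conditions. Safety guidance should not depend on the reader rejecting the nearest antecedent.

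**Conclusion.** The point holds as a misplaced reference in operative safety guidance. Read in order, Appendix 6 gives unconditional encouragement where Sections 3.5 and 4.5.6 give conditional permission. Those sections still govern, so the stopping rules themselves are unchanged.

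The size is unknown and probably small. It concerns only subjects who have an optional biopsy that shows progression and whose site follows the bullet without going back to the main text. The documents give no count. The flare frequencies quoted in Appendix 6 (10% in melanoma, 3% in lung cancer) are for other tumors and do not measure biopsy-confirmed progression, so they cannot be used to estimate one.

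The conclusion rests on two assumptions: that sites read the bullets in sequence, and that the unpublished parts of the protocol do not already clarify the sentence. The change is worth making because the literal advice touches patient safety and the correction is almost free. The Section 4.5.1 omission is a consistency matter only. Response rate and sample size are unaffected by either.

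**What to change.** In Appendix 6, attach the resume sentence directly to the necrosis and inflammation finding, so that the cases meant are those in which the biopsy supports flare. Then add: *If biopsy confirms tumor progression, follow Sections 3.5 and 4.5.6: discontinue unless all treatment-beyond-progression criteria, including written consent, are met.*

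In Section 4.5.1, add to the stopping conditions for 480 mg dosing: *or a maximum of 2 years of total treatment.*

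The cost is one moved sentence, one added sentence and one added phrase. An administrative letter or the next amendment would do. SAP Table 2.4-1 shows that Administrative Letter 06 already corrected the same part of Appendix 6, so there is a precedent. Design, sample size and analysis stay as they are.
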